#### 13.5

##### Method of Assessment of EGFR Expression in Tumor After Cetuximab

##### Loading Dose

At the time of the second biopsy, four core biopsies from different areas of the tumor as well as swab of the normal appearing mucosa will be obtained. Four core biopsies will be processed with one core used in high-throughput immunoblot analysis, one core will be fixed in formalin to be embedded in paraffin, one core will be frozen and fixed in Tissue-Tek OCT for immunofluorescence analysis and one core will be used for RNA and DNA isolation using Trizol. EGFR phosphorylation analysis using immunoblotting and immunohistochemistry will be performed in the surgical specimen and immunofluorescence analysis will also be performed if sufficient tissue is available using standard methods. Interpretations of the staining will be performed according to the standard guidelines. The EGFR and critical associated down-stream signaling pathways will be analyzed post- induction therapy, including p-EGFR and total EGFR, p-ERK1/2, p-AKT, p27, Ki-67, and p-STAT3, and other markers that we may discover in our preclinical studies. EGFRvIII expression and p53 mutation analysis will be assessed on cDNA obtained from total RNA converted with RT-PCR. Genomic DNA from the tumor biopsy will be used to test for HPV presence and type as carried out by PCR-mass spect using the AttoSense assay at SensiGen, LLC.

#### 14.0 Other Therapy

All supportive therapy for optimal medical care will be given during the study period at the discretion of the attending physician(s) within the parameters of the protocol and documented as concomitant medication.

## **15.0 Informed Consent**

**15.4** All patients with squamous carcinoma of the head and neck, who are candidates for definitive radiation, will be screened for participation in this study.

**15.5** Alternative treatment options include chemoradiation, radiation therapy alone, or palliative chemotherapy.

**15.6** Patients who meet the inclusion criteria will be approached for possible participation in this study. The nature of the investigation will be described to the patient including the risks and side effects of study treatments, the potential benefit of the study to themselves and others, the time commitment and frequency of patient visits and the clinical evaluations they will be required to undergo. The patient will then have the opportunity to ask questions. The patient will be given the IRB approved informed consent form for consideration. Each patient will be allowed to read (or have read to them) the informed consent form and understand before discussing consent with the investigator. If consent to participate is granted, the patient's signature will be obtained on the informed consent form. The original form will be kept in the patient's research chart and a copy will be given to the patient.

## **16.0 Patient Registration**

Patient registration for this trial will be centrally managed by the Clinical Trials Office of The University of Michigan Comprehensive Cancer Center as described below:

A potential study subject who has been screened for the trial and who has signed the Informed Consent document will be initially documented by the participating site on the Screening and Enrollment Log provided by the Clinical Trials Office.

It is the responsibility of the local site investigator to determine patient eligibility prior to submitting patient registration request to the Clinical Trials Office. After patient eligibility has been determined, a copy of the completed Eligibility Worksheet together with all the pertinent de-identified source documents will be submitted by the requesting site to the Clinical Trials Office, either by fax or by email to [REDACTED]

A Multi-Site Coordinator of the Clinical Trials Office, who acts as the registrar, will review the submitted documents and process the registration. Sites should inform the Multi-Site Coordinator of a potential registration by 5 p.m. on the day prior to registration. Same day registrations cannot be guaranteed.

An email will be sent by the registrar to the requesting site registrar to confirm patient registration and to provide the study identification number that has been assigned to the patient. In addition, a copy of the completed Section Two of the Eligibility Worksheet signed and dated by the registrar, will be faxed back to the requesting site registrar.

Patients found to be ineligible for participation after being consented will be considered screen failures, and documented as such in the Screening and Enrollment Log. These

patients will not have study identification number assigned to them, and will not receive study treatment

## **17.0 Adverse Drug Events**

### **1.**

Adverse event (AE) monitoring and reporting is a routine part of every clinical trial. Data on adverse events will be collected from the time of the initial investigational agent administration through the two year study. Serious Adverse Events (SAEs) will continue to be followed until resolution or clearly determined to be due to a patient's stable or chronic condition or intercurrent illness(es).

The investigator is responsible for the detection and documentation of events meeting the criteria and definition of an AE or SAE. The definitions of AEs and SAEs are given below. It is the responsibility of the principal investigator to ensure that all staff involved in the trial is familiar with the content of this section.

Any medical condition or laboratory abnormality with an onset date before agent administration is considered to be pre-existing in nature. Any known pre-existing conditions that are ongoing at time of study entry should be considered medical history.

All adverse events occurring from the initial investigational agent administration through the two year study calendar must be recorded as an adverse event in the patient's source documents regardless of frequency, severity (grade) or assessed relationship to the investigational agent/intervention. In addition to new events, any increase in the frequency or severity (i.e., toxicity grade) of a pre-existing condition that occurs after the patient begins taking the investigational agent/intervention is also considered an adverse event. All moderate events (grade 2) and hematologic serious events (grade 3) due to the patient's cancer or the treatment which are common toxicities and expected will be excluded from this data collection. These will be noted in the patient's medical records.

All adverse events specified in the Case Report Form Completion Guidelines will be recorded in the study database (Velos)

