21.3.3 **Primary Objective 3** *Describe the toxicity, in particular mucositis/dysphagia, of this regimen.* Adverse events will be tabulated by grade (NCI CTCAE v4), category (mucositis and dysphagia are expected to be the most common) and relatedness to treatment (not, unlikely, possibly, probably or definitely). The proportion of patients experiencing Grade 3 or worse adverse events at least possibly related to treatment will be calculated, accompanied by a 95% exact binomial confidence interval. Possible baseline demographic and clinical predictors of such toxicity may be evaluated by means of logistic regression, but, due to the low expected number of such toxicities, any such modeling will be strictly exploratory.

21.3.4 **Secondary Objective 1** *Conduct normal mucosa EGFR assessment for comparison with tumor sample.* The change in tumor EGFR level across treatment, relative to EGFR in normal mucosa, will be evaluated by means of repeated measures ANOVA.

21.3.5 **Secondary Objective 2** *Correlate HPV presence and titer with p53 status and clinical outcome.* HPV status ( $\pm$ ) will be added to the models of Primary Objective 2 to determine if +HPV patients respond to therapy differently than -HPV patients, but, due to the limited expected number of +HPV patients, such analyses will be considered exploratory.

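### Section 17.0 drops common, expected Grade 2 and Grade 3 haematologic events from adverse event collection, but the toxicity analysis in 21.3.3 counts them and names no data source

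*Combined protocol and SAP*

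**What the plan says.** Section 17.0 sets out four rules on adverse events.

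- Period: "Data on adverse events will be collected from the time of the initial investigational agent administration through the two year study".
- Source record: every event in that period goes into "source documents regardless of frequency, severity (grade) or assessed relationship to the investigational agent/intervention".
- Exclusion: "All moderate events (grade 2) and hematologic serious events (grade 3) due to the" cancer or its treatment, "which are common toxicities and expected will be excluded from this data collection". These events are noted only in the medical record.
- Database: "All adverse events specified in the Case Report Form Completion Guidelines will be recorded in the study database (Velos"). Those guidelines are not part of the documents.

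Section 21.3.3 covers Primary Objective 3, the description of toxicity with emphasis on mucositis and dysphagia (2.1.3). It plans two things.

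- A table: "Adverse events will be tabulated by grade (NCI CTCAE v4), category (mucositis and dysphagia are expected to be the most common"). Attribution is its third dimension, on a five-level scale that runs from unrelated to definitely related.
- An estimate: "The proportion of patients experiencing Grade 3 or worse adverse events at least possibly related to treatment will be calculated", with an exact 95% binomial interval.

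It mentions neither the exclusion in 17.0 nor the data on which the table and the estimate will be built.

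**The concern.** The collection rule removes events that the analysis rule counts. Mucositis and dysphagia are the toxicities of most interest, and 21.3.3 expects them to be the most frequent. At Grade 2 they are therefore natural candidates for an exclusion aimed at common, expected toxicity. Section 11.8 already lists stomatitis and mucous membrane disorder for cetuximab. The Grade 3+ proportion is exposed in a different way: it loses any patient whose sole qualifying event is an expected Grade 3 haematologic one.

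Section 1.0 presents the study as part of a search for less toxic treatment in older and frailer patients. A toxicity table made lighter by a collection rule would bear directly on that question, and a reader of 21.3.3 would have no sign that it had happened.

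**Working it through.** **The two rules side by side.** The plan gives no expected toxicity rate or precision to reproduce, so the main check compares the texts. For events due to treatment, read literally:

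| Event | 17.0 data collection | 21.3.3 table by grade | 21.3.3 Grade 3+ proportion |
|---|---|---|---|
| Grade 1 | kept | counted | not relevant |
| Grade 2, common and expected | **excluded** | counted | not relevant |
| Grade 3 haematologic, common and expected | **excluded** | counted | counted |
| Grade 3 non-haematologic, including mucositis and dysphagia | kept | counted | counted |
| Grade 4 or worse | kept | counted | counted |

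Rows 2 and 3 conflict. Row 2 affects only the table: a mucositis line could show Grades 1, 3 and 4 with Grade 2 missing. Row 3 affects both outputs. Removing events cannot add a patient to the Grade 3+ numerator, so any error there is downward.

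**Effect on the Grade 3+ proportion.** The denominator is 50 evaluable patients (21.2), so one lost patient costs 1/50 = 2.0 points. The exact interval for x of n runs from the 0.025 quantile of Beta(x, n−x+1) to the 0.975 quantile of Beta(x+1, n−x). Section 21.3.3 expects few such toxicities but gives no number, so counts of 5 and 10 are assumed.

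| All events captured | One patient lost |
|---|---|
| 5/50 = 10% (3.3% to 21.8%) | 4/50 = 8% (2.2% to 19.2%) |
| 10/50 = 20% (10.0% to 33.7%) | 9/50 = 18% (8.6% to 31.4%) |

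**When the loss would matter.** Let c be the rate seen in the collected data and h the share of patients whose only related Grade 3+ event is an excluded one. The chance that the reported interval contains the full rate c + h is the sum of Binomial(x; 50, c) over all x whose exact interval contains c + h. The values of c come from Section 1.0, which reports another trial in another population: Grade 3–4 mucositis of 24% with radiotherapy alone and 43% with concurrent chemoradiotherapy, and high-grade toxicity of 61% with radiotherapy alone. The values of h are assumed.

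| c | h = 0 | 2 points | 4 | 6 | 10 | 20 |
|---|---|---|---|---|---|---|
| 24% | 97.0% | 96.3% | 93.4% | 87.9% | 68.2% | 20.1% |
| 43% | 95.6% | 94.7% | 92.0% | 87.2% | 71.4% | 19.5% |
| 61% | 95.9% | 94.9% | 92.2% | 87.5% | 72.1% | 12.2% |

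At c = 24% and h = 10 points, the report would show 12/50 = 24% (13.1% to 38.2%) where full capture gives 17/50 = 34% (21.2% to 48.8%). The effect is negligible up to about 2 points and material from about 6 to 10 points.

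**The case against.** The strongest reply is that 21.3.3 never says it uses the Section 17 data. Section 7.6.5 separately collects CTCAE v4 items before, during and after radiation with no grade exclusion. Section 8.0 schedules toxicity evaluations before treatment, weekly during radiation, at 1 month, at 12–14 weeks and through year 2. Section 7.4.2 has all patients assessed weekly in relation to mucositis. Every event also stays in the source documents, and weekly blood counts would show haematologic toxicity. The CRF Completion Guidelines, which were not available for this review, may already settle the matter.

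The haematologic part may also be empty. Section 11.8 lists only leukopenia, and the definition of an unexpected event in 17.1 includes one more severe than listed. A 2-point shift lies well inside intervals 17 to 24 points wide, and the objective is descriptive.

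Much of this stands. The 7.6.5 evaluations may recover most Grade 2 mucositis and dysphagia, and the number of haematologic-only patients may be zero. The conflict remains for these reasons:

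- Section 21.3.3 does not cite the evaluations or call for chart abstraction.
- Neither 7.6.5 nor 8.0 says that relatedness is recorded, and 21.3.3 needs it.
- The calendar has no toxicity evaluation or blood count on Day 0 or Day 7, and scheduled visits can miss events between them.
- Section 17.0 itself contemplates expected Grade 3 haematologic events and gives no list of what is common or expected, so sites may apply the rule differently.

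**Conclusion.** The concern holds. A stated collection rule, followed literally, removes events that a primary-objective analysis counts, and the analysis section neither repeats the exclusion nor names another source. The cost to the Grade 3+ rate is 2.0 points for each affected patient out of 50, always downward; the number affected cannot be found from the documents. The loss of Grade 2 events from the table cannot be sized. Grade 3+ mucositis and dysphagia and Grade 4 haematologic events are not excluded.

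The consequences assume that 21.3.3 draws on the Section 17 data. The protocol and SAP do not settle that; the CRF Completion Guidelines and the investigator brochure might. Confidence in the practical effect is therefore medium. With no stopping rule for toxicity (21.4), what is at risk is the accuracy of the reported toxicity. The mismatch should be corrected, but it does not threaten the conduct of the trial.

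**What to change.** 1. In 17.0, exempt two groups from the exclusion: any CTCAE v4 event of Grade 3 or worse, haematologic events included; and mucositis or dysphagia of any grade. Record relatedness for these events on the five-level scale of 21.3.3.
2. In 21.3.3, name the data source: the Section 17 adverse event record from first administration through two years, supplemented by the toxicity evaluations of 7.6.5 and 8.0 and the blood count results. The Section 17 record should stay the base, because the scheduled evaluations skip Day 0 and Day 7 and can miss events between visits.
3. In 21.3.3, state that other expected Grade 2 events are not collected and so do not appear in the table.
4. Bring the CRF Completion Guidelines into line.

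If the sponsor prefers to keep the exclusion as it is, 21.3.3 should state it and restrict the table and the Grade 3+ proportion accordingly. That would make the plan consistent but could leave the description of mucositis and dysphagia incomplete at Grade 2.

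The cost is wording in two sections, a check of the CRF guidelines, and modest extra data entry and attribution for events already held in source documents. No visits or tests are added.

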### **17.1 Definitions**

#### **Adverse event**

Adverse event means any untoward medical occurrence associated with the use of a medical treatment or procedure regardless of whether or not considered related to the medical treatment or procedure.

An adverse event (also referred to as an adverse experience) can be any unfavorable and unintended sign (e.g., an abnormal laboratory finding), symptom, or disease temporally associated with the use of a medical treatment or procedure, without any judgment about causality.

#### **Unexpected**

An adverse event or suspected adverse reaction is considered “unexpected” if it is not listed in the investigator brochure or is not listed at the specificity or severity that has been observed; or, if an investigator brochure is not required or available, is not consistent with the risk information described in the general investigational plan or elsewhere in the current application. For example, under this definition, hepatic necrosis would be unexpected (by virtue of greater severity) if the investigator brochure referred only to elevated hepatic enzymes or hepatitis. Similarly, cerebral vasculitis would be unexpected (by virtue of greater specificity) if the investigator brochure listed only cerebral vascular accidents. "Unexpected," as used in this definition, also refers to adverse events or suspected adverse reactions that are mentioned in the investigator brochure as occurring with a class of drugs or as anticipated from the pharmacological properties of the drug, but are not specifically mentioned as occurring with the particular drug under investigation.

### **Serious Adverse Event**

An adverse event or suspected adverse reaction is considered “serious” if, in the view of either the investigator or sponsor (UNIVERSITY OF MICHIGAN), it results in any of the following outcomes:

- Death
- A life-threatening adverse event
- Inpatient hospitalization or prolongation of existing hospitalization
- A persistent or significant incapacity or substantial disruption of the ability to conduct normal life functions
- A congenital anomaly/birth defect.
- Important medical events that may not result in death, be life-threatening, or require hospitalization may be considered serious when, based upon appropriate medical judgment, they may jeopardize the patient or subject and may require medical or surgical intervention to prevent one of the outcomes listed in this definition. Examples of such medical events include allergic bronchospasm requiring intensive treatment in an emergency room or at home, blood dyscrasias or convulsions that do not result in inpatient hospitalization, or the development of drug dependency or drug abuse.

Previously planned (prior to signing the informed consent form) surgeries should not be reported as SAEs unless the underlying medical condition has worsened during the course of the study. Preplanned hospitalizations or procedures for preexisting conditions that are already recorded in the patient’s medical history at the time of study enrollment should not be considered SAEs. Hospitalization or prolongation of hospitalization without a precipitating clinical AE (for example, for the administration of study therapy or other protocol-required procedure) should not be considered SAEs. However, if the preexisting condition worsened during the course of the study, it should be reported as an SAE.

### **Life-threatening**

An adverse event is considered “life-threatening” if, in the view of either the investigator or sponsor, its occurrence places the patient or subject at immediate risk of death. It does not include an adverse event that, had it occurred in a more severe form, might have caused death.

### **18.1 Exceptions to SAE Reporting**

The following adverse events are excluded from SAE reporting:

- Hospitalization secondary to expected cancer morbidity
- Admission for palliative care or pain management
- Planned hospitalizations for surgical procedures either related or unrelated to the patient's cancer.
- Emergency Department visits not related to study treatment

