#### 12.11

##### Treatment Interruptions:

It is expected that the entire treatment for definitive irradiation will be completed in about 7-8 weeks. Treatment interruptions due to symptomatic mucositis or skin reactions are rare. In the case of severe mucositis, preventing appropriate nutritional intake, a gastric tube or dohoff tube will be inserted and radiation will continue uninterrupted at the discretion of the treating physician. Weight will be recorded weekly in the Radiation Oncology chart. If the patient's weight loss exceeds 10% of the initial weight or if the patient is malnourished before radiation, a feeding tube may be inserted by an appropriately trained physician (surgeon, gastroenterologist, interventional radiologist) as defined by clinical practice.

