### **19.0 Data and Safety Monitoring**

The Data and Safety Monitoring Board (DSMB) of The University of Michigan Comprehensive Cancer Center (UMCCC) is the DSMB for this study. This committee is responsible for the review and monitoring the study's scientific progress, accrual rate and any serious adverse events.

Each participating site is required to have its own Data and Safety Monitoring Committee (DSMC) for the study. This committee will be composed of the local site principal investigator, site co-investigator(s), site data manager or study coordinator and other members of the study staff involved in the conduct of the trial. During the committee's bimonthly meeting, the principal investigator will discuss matters related to:

- Enrollment rate relative to expectations, characteristics of participants
- Safety of study participants (Serious Adverse Event & Adverse Event reporting)
- Adherence to protocol (protocol deviations)
- Completeness, validity and integrity of study data
- Retention of study participants

These meetings are to be documented by the site data manager or study coordinator using the Protocol Specific Data and Safety Monitoring Report (DSMR), signed by the site principal investigator or co-investigator. Each site is required to submit the completed DSMR to the Multi-Site Coordinator at the University of Michigan Clinical Trials Office on a quarterly basis together with other pertinent documents.

Similarly, protocol deviations are to be documented using the Notice of Protocol Deviation Form and requires the signatures of both the sites data manager or study coordinator and the site principal investigator [or co-investigator]. These reports are to be sent to the University of Michigan Clinical Trials Office within 7 calendar days of awareness of the event and on a quarterly basis with the Protocol Specific Data and Safety Monitoring Report.

The Clinical Trials Office is responsible for collating all the Data and Safety Monitoring Reports from all the participating sites, and providing the information to the Data Safety Monitoring Board.

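### Section 18.1 exempts pain-management and planned surgical admissions from SAE reporting without a treatment-relatedness limit, and is broader than the SAE definition in section 17.1

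*Combined protocol and SAP*

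**What the plan says.** Under Serious Adverse Event, section 17.1 treats an adverse event as serious if, in the view of the investigator or the sponsor, it results in "Inpatient hospitalization or prolongation of existing hospitalization". It then makes three exemptions:

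- Surgery: "Previously planned (prior to signing the informed consent form) surgeries should not be reported as SAEs unless the underlying medical condition has worsened".
- Preplanned admissions or procedures for pre-existing conditions already in the medical history.
- Admissions with no clinical adverse event behind them, such as those made to give study therapy.

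Section 18.1 sets four exclusions:

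- The first is tied to the cancer as the cause: "Hospitalization secondary to expected cancer morbidity".
- The second is not tied to any cause: "Admission for palliative care or pain management".
- The third concerns surgery and sets no date by which it must have been planned: "Planned hospitalizations for surgical procedures either related or unrelated to the patient's cancer".
- The fourth is the only one that mentions study treatment: "Emergency Department visits not related to study treatment".

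Other relevant places are:

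- Sections 2.1.3 and 21.3.3 (Primary Objective 3) single out mucositis and dysphagia as the toxicities to describe.
- Section 12.11 says that in severe mucositis that prevents adequate nutrition "a gastric tube or dohoff tube will be inserted and radiation will continue uninterrupted", at the treating physician's discretion.
- Section 19.0 makes the DSMB responsible for "monitoring the study's scientific progress, accrual rate and any serious adverse events".

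**The concern.** The fourth exclusion shows that the authors knew how to limit an exception to events unrelated to treatment. The pain and surgery exclusions carry no such limit, and the surgery exclusion does not say when the procedure must have been planned. Read literally, they cover admissions that the regimen itself caused.

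Mucositis is painful, and it is one of the two toxicities named in Primary Objective 3. A patient admitted for control of treatment-caused mucositis pain has an SAE under 17.1 and an excluded event under 18.1. Registration and monitoring provide for several participating sites (sections 16.0 and 19.0), so the same admission could be classified differently depending on which section a site follows.

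SAE review matters here. Section 21.4 provides no rule for halting the trial for excess toxicity, and the patients are enrolled because they are poor candidates for chemoradiation.

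**Working it through.** The core of this point is textual, and the plan gives no figure to reproduce. The check is to take each kind of admission through both sections.

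| Admission after the first cetuximab dose | Section 17.1 | Section 18.1 |
|---|---|---|
| Unplanned, for pain from treatment-caused mucositis | SAE: an adverse event led to hospitalization and no exemption fits | Excluded as pain management, whatever the cause |
| Planned after consent, inpatient, for surgical feeding-tube placement because of severe mucositis | SAE: not planned before consent, and a clinical adverse event precipitated it | Can be excluded as planned surgery |
| Unplanned, for treatment-caused dehydration, aspiration or infection | SAE | No exclusion fits, so still reportable |
| For expected morbidity of the cancer itself | SAE if an adverse event led to hospitalization | Excluded, but the cancer must be the cause |

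The sections give different answers in rows 1 and 2 for events caused by study treatment. Row 1 follows directly from the text. Row 2 is conditional: section 12.11 does not say that tube placement needs a planned surgical admission. It allows a nasally or gastrically placed tube, and it names a gastroenterologist or interventional radiologist as well as a surgeon as possible operators. Row 3 is unaffected. In row 4 the exclusion already carries its own causal limit.

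Next, what is lost downstream:

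- **Primary Objective 3.** Section 21.3.3 tabulates adverse events by grade, category and relatedness. It estimates the proportion of patients with Grade 3 or worse events at least possibly related to treatment, with an exact 95% interval. SAE status does not enter. The data-collection exclusion in section 17.0 covers common expected Grade 2 events and hematologic Grade 3 events, so Grade 3 mucositis or dysphagia is still recorded.
- **DSMB.** Under section 19.0, site meetings cover both serious and other adverse events. Their reports go to the Clinical Trials Office quarterly, which collates them for the DSMB. The event may therefore reach the DSMB, but not as an SAE.

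An illustration of size. Inputs: 50 evaluable patients (section 21.2), and Grade 3 to 4 mucositis of 24% with radiotherapy alone and 43% with concurrent chemoradiotherapy (section 1.0). The share admitted for pain or a planned tube is not in the documents; 20% to 50% is assumed.

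- Patients with severe mucositis: 0.24 × 50 = 12, and 0.43 × 50 = 21.5.
- Admitted, low end: 12 × 0.20 = 2.4.
- Admitted, high end: 21.5 × 0.50 = 10.75.
- Radiotherapy-alone rate only: 12 × 0.20 = 2.4 to 12 × 0.50 = 6.

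This gives about 2 to 11 patients, or about 2 to 6 at the lower mucositis rate. Neither source arm received cetuximab, and the sum assumes that every such admission is placed under an exclusion.

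**The case against.** The strongest reply is that 17.1 defines seriousness while 18.1 sets exceptions to reporting, and exceptions that cut back a definition are normal drafting. That explains why 18.1 exists, but not the conflict. If 18.1 overrides, the pre-consent limit on planned surgery in 17.1 has no effect, and treatment-caused pain admissions are excluded throughout. If 17.1 governs, 18.1 misleads the sites.

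A second reply is that the consequences are contained, because the toxicity analysis uses graded adverse events, the site reports cover them, and no halting rule depends on an SAE count. This stands and sets the limits of the point. The absence of a halting rule cuts both ways, since it leaves more of the safety oversight to SAE review.

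A reader might go further and infer that admissions for severe mucositis or dysphagia are, as a class, not reported as SAEs. The documents do not support that. Section 18.1 names neither condition, and unplanned admissions for dehydration, aspiration or infection fit none of its exclusions. Filing treatment-caused dysphagia under cancer morbidity would be a misclassification, not something the text permits. Nor do the documents support the inference that the primary toxicity result would understate the regimen's toxicity, since that result does not use SAE reports.

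One limit remains. The text available for this review passes from 17.1 to 18.1 without the body of section 18.0 (Reporting Procedures), so an overriding rule there could not be checked for.

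**Conclusion.** The point holds in a limited form. Two of the four exceptions in 18.1 lack the treatment-relatedness limit given to emergency visits and go beyond what 17.1 exempts. As written, admissions for treatment-caused mucositis pain would not be reported as SAEs. Planned feeding-tube admissions might not be either, if placement involves a planned surgical admission. What is lost is the classification and reporting of these admissions as serious, not the record of the underlying Grade 3 or worse event.

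The number affected cannot be derived from the documents. The range of about 2 to 11 patients in 50 is an illustration that rests on an assumed admission rate and on mucositis rates from arms without cetuximab. The conflict between the sections does not depend on it. The conclusion does assume that the body of section 18.0 contains no overriding rule for treatment-related events. The correction is worth making because it is cheap and improves safety reporting in a vulnerable population.

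**What to change.** Reconcile 18.1 with 17.1 in an amendment with two added sentences:

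1. The exceptions for palliative-care or pain-management admissions and for planned surgical admissions apply only when the admission is not at least possibly related to cetuximab, radiation or a research procedure. The threshold of at least possibly related is already used in section 21.3.3.
2. The planned-surgery exception covers only surgery planned before consent, and does not apply if the underlying condition has worsened, as in 17.1.

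Check the body of section 18.0 at the same time, so that it agrees with both sections. The cost is the amendment and a few more SAE forms for admissions already in the source documents. No added visit, procedure or analysis is needed.
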